6. INTRODUCTION

6.1 Background

Erectile dysfunction (ED) is a chronic condition affecting male sexual function and has a significant health economic impact worldwide. It has been surmised that if all men in the United States (US) sought care for ED, the cost of treatment in the US alone would reach \$15 billion [1]. Although it can affect all age groups, the frequency of ED increases with age. The probability of ED triples from 5% in men aged 40 years to 15% in men aged 70 years [2]. A recent study which evaluated ED in men aged 40–79 years suggested that the prevalence of ED was highest in men aged 70 years or older [3]. When adjusted for age, patients with cardiovascular disease and diabetes have an increased risk of ED [4]. Given the increase in life expectancy across the western world coupled with higher frequencies of cardiovascular disease and diabetes, it is predicted that by 2025 the global prevalence of ED will be approximately 322 million, which could contribute to a significant cost burden on healthcare systems [5].

ED is a multi-factorial condition with a treatment trajectory compounded because aging men are often affected with several diseases, leading to polypharmacy and treatment regimens that could potentially worsen the ED. According to the National Institutes of Health (NIH) Consensus Development Conference, ED can be defined as ‘the persistent inability to achieve or maintain penile erection sufficient for satisfactory sexual performance’ [6]. In view of this definition, the NIH also recommends the use of ‘erectile dysfunction’ as the agreed term instead of ‘impotence’.

The treatment of ED usually follows a circuitous route. Erectile function (EF) involves a complex coordination of physiological processes and as such the management of ED reflects this complexity. Evidence suggests that 80% of ED cases are of organic origin [6]. These organic causes are diverse and include, but are not limited to, vascular disorders (such as cardiovascular disease, hypertension), iatrogenic factors (such as hormonal agents, beta-blockers), penile injury/anatomic abnormalities (such as Peyronie's disease, priapism) and endocrine disorders (such as diabetes, hypogonadism). The most frequent organic causes of ED are thought to be vascular in origin and patients frequently present with decreased blood flow to the penis owing to cardiovascular disease [7]. Many cases of ED are characterised as ‘vascular’ indicating a correlation with cardiovascular risk factors and events [8].

Usually, first-line therapies for the treatment of ED are lifestyle changes (exercise and weight loss) and modifications to risk factors [9], followed by treatment with oral phosphodiesterase type 5 (PDE-5) inhibitors such as sildenafil, tadalafil or vardenafil [10]. Other treatments such as intracavernosal injections [11] and intraurethral suppositories have been used previously; however, these treatments are frequently associated with adverse events (AEs) such as local pain and priapism and poor compliance owing to their invasive nature [12]. Topical prostaglandin E1 (PGE 1) has been used for the treatment of ED [13]. In one study, the treatment was safe, well-tolerated and significantly increased penile blood flow in 8 patients. The treatment has gained popularity owing to its ease of use [14], and the topical administration of alprostadil (a synthetic form of PGE 1) is licensed for the treatment of ED in men aged ≥ 18 years [15]. Owing to their less invasive routes of administration and ease of use, topical therapies approved for other indications have been explored as alternative candidates for the treatment of ED.

Although PDE-5 inhibitors are widely used in ED and their side-effects have been well documented, all PDE-5 drugs are contraindicated in patients taking nitrates (such as glyceryl

trinitrate [GTN], a potent smooth muscle vasodilator) for cardiovascular disease. From an epidemiological perspective this fact has broader implications given the putative link between ED and cardiovascular disease in the elderly.

The vasodilator GTN is a well-known and well documented therapeutic agent. GTN has established clinical use for the prophylaxis of angina. It is usually administered inter-nasally, orally or sublingually as short- or long-acting tablets and sprays, or transdermally via patches or topical ointments. Clinical data for nitric oxide (NO) donors and their impact on ED is less extensive compared with PDE-5 inhibitors; however, available evidence suggests that NO donors, for example topically applied GTN, might be a potentially useful approach to the management of sexual dysfunction [16]. Topical GTN is also licensed for the treatment of anal fissure.

The first case of an organic nitrate improving ED was reported in 1977 in a patient taking sublingual GTN. Since then, several studies have shown that GTN (either as a topical ointment at concentrations ranging from 2 to 10%, or as a topical plaster) is effective in increasing penile tumescence in patients with organic, psychogenic or mixed ED with no significant differences between ED subtypes [17]. Whilst so far there is little empirical evidence on the effect of topical GTN on ED, one study has shown that topical application of a cream containing the NO donor, isorbide dinitrate, is efficacious [18]. In a randomised, double-blind, placebo-controlled study, 21 out of 36 men with ED reported full erection and satisfactory intercourse after 1 week of treatment with an active cream containing aminophylline 3%, isosorbide dinitrate 0.25% and co-dergocrine mesylate 0.05% versus placebo. There were no cases of priapism or significant AEs, and none of the 21 subjects reported complaints from their partner.

6.2 Rationale for Conducting Study

In light of the recent literature, Futura Medical Developments Ltd (FMD) are developing a gel formulation of GTN (MED2005) as a topical treatment for ED delivered using DermaSys®, a versatile and bespoke technology. Of particular interest are subjects who are currently taking chronic oral nitrate therapy, for whom the use of oral PDE-5s are contraindicated.

FMD has conducted three Phase I, dose-ranging clinical studies with MED2005: a pharmacokinetic (PK) study (Study FM33), a pharmacodynamic (PD) study (FM35), which used penile blood flow changes as a surrogate marker of efficacy; a second PK study (Study FM58) and one Phase IIa study in male subjects clinically diagnosed with ED (Study FM53). In view of the results of these studies (see Section 6.3 below), FMD is further developing MED2005 for the intended treatment of ED in male subjects

6.3 Clinical Studies with MED2005

For further details of the clinical studies carried out with MED2005, please refer to the current version of the FMD MED2005 Clinical Investigator's Brochure (IB).

6.3.1 Pharmacokinetics

The Phase I PK study (FM33) demonstrated a dose-response relationship with regard to plasma levels of GTN in 16 healthy male volunteers. The time to reach the maximum plasma concentration (t_{max}) ranged between 6.5 and 9.0 minutes, and the terminal elimination half-life ($t_{1/2}$) was approximately 4 minutes. The second Phase 1 PK study (FM58 PK), the CSR for which has yet to be finalised, demonstrated a dose response relationship with regards to plasma levels in 30 healthy male volunteers. The t_{max} ranged between 10-12 minutes. The data

suggested that MED2005 doses in the range of 0.2%-0.6% may be optimum for further efficacy and safety studies.

6.3.2 Pharmacodynamics

The Phase I volunteer study (FM35) has shown evidence of PD effects supportive of the intended indication. This single-centre, placebo-controlled, double-blind, dose-ranging, crossover study assessed the physiological effects of GTN gels on application to the glans penis in 15 healthy male volunteers. The study, which used Doppler ultrasound to measure penile blood flow, was not powered to produce statistically significant outcomes. However it provided a complex data set from which the following conclusions were drawn:

- MED2005 appeared to stimulate penile blood flow in a number of subjects relative to placebo
- Some vascular changes (penile artery, peak systolic velocity, end diastolic velocity) achieved statistical significance with certain doses at certain time points
- MED2005 at a dose of 0.6 mg appeared to induce a greater effect on blood flow than any of the other doses used
- [name], a Consultant at Kings College Hospital, London and an expert in the use of Doppler ultrasound, commented that the blood flow changes induced by MED2005 were consistent with the erection process and therefore that these data were encouraging in regard to GTN's proposed erectogenic action

6.3.3 Efficacy and Safety

The efficacy and safety of MED2005 was assessed in a recent Phase IIa, multi-centre, randomised, double-blind, placebo-controlled, crossover study in male subjects clinically diagnosed with ED (Study FM53). The application of 0.6 mg MED2005 gel to the glans penis was associated with a statistically significant increase (i.e. improvement) in the EF domain score of the International Index for Erectile Function (IIEF; the primary endpoint) compared with a placebo gel. The efficacy of MED2005 compared with placebo was further supported by the analyses of the secondary efficacy outcome variables.

The tolerability and safety profile of MED2005 appears to be predictable and consistent with the known pharmacological profile of GTN. In Study FM53, 15 mild related headaches were reported in 1023 intercourse attempts and only 2 mild related headaches were reported by the female partners.

The Phase I, healthy volunteer studies FM33, FM35 and FM58 demonstrated a favourable safety profile of MED2005. There was a low incidence of mild transient headache, no clinically significant effects on blood pressure (BP) and no serious adverse events (SAEs). In the Phase IIa study in male subjects clinically diagnosed with ED (FM53), a locally applied dose of MED2005 was considered safe, well-accepted and well-tolerated by the male subjects and their female partners. FMD has also conducted a single-blind, placebo-controlled, dose-ranging study to assess the physiological effects and tolerability of a different GTN gel formulation (Zanafil) applied to the vaginas of a group of healthy, pre-menopausal, female volunteers (Study FM22). No AEs were reported following vaginal application of 0.5 mg and 1 mg doses of GTN gel. This suggests that even if the full dose of MED2005 was transferred to the female partner during sexual intercourse, it would be unlikely to cause any notable tolerability problems.

For further safety information, please refer to the 'Reference Safety Information' of the current version of MED2005 IB.

Additional studies in subjects with ED are required to further demonstrate the efficacy and safety of MED2005. This is the reason for the current study.

6.4 Risk-Benefit Evaluation

6.4.1 Potential Benefits

MED2005 is being developed for the treatment of ED and as such, subjects receiving treatment with MED2005 might benefit from improvements in EF and quality of life for themselves and their partners.

6.4.2 Potential Risks

Preclinical studies demonstrate that GTN does not possess teratogenic potential, has no adverse effects on male or female reproductive organs and is unlikely to have the potential to cause sensitisation or irritation at the intended site of application in men or women.

Published clinical studies and literature reports confirm the pharmacologically predictable tolerability profile of GTN. The most common AEs that have been reported are headache (generally mild and short-lived) and hypotension (not normally symptomatic). The literature reports relative success following the application of GTN transdermal patches or GTN ointment to the shaft of the penis.

GTN has been used in clinical practice in numerous countries for more than 100 years for the treatment of angina pectoris and other cardiovascular conditions. The side-effects of GTN are well documented and reports indicate that the most common undesirable effects include headache, facial flushing and nausea. In subjects treated with GTN ointments, for example for rectal pain or angina prophylaxis, the reported AEs are similar to those documented for other GTN treatments. For the treatment of rectal pain, the most commonly reported treatment-related AEs using Rectogesic® 4 mg/g rectal ointment were dose-dependent increases in headache (57% of subjects) followed by dizziness and nausea [19]. For prophylaxis of angina pectoris, AEs related to Percutol® 2% ointment have also been shown to be dose-related and almost all were the result of vasodilator activity. Headache was the most commonly reported AE [20]. Other commonly reported AEs with GTN 2% ointment include nausea and vomiting. Uncommon side-effects include cardiac disorders (tachycardia, bradycardia [in the presence of syncope]), vascular disorders (hypotension, circulatory collapse), allergic skin disorders (eczema, dermatitis, pruritus, urticaria, non-specific rashes) and immune system disorders (hypersensitivity reactions, anaphylaxis).

The study is designed for careful monitoring of any potential AEs of MED2005.

6.5 Conduct of the Study

This study will be performed in compliance with the protocol, International Council for Harmonisation (ICH) Good Clinical Practice (GCP) and applicable regulatory requirements including European Union (EU) Good Manufacturing Practice (GMP) requirements for investigational medicinal products (IMPs).

7. STUDY OBJECTIVES

7.1 Primary Objective

- To demonstrate the efficacy of MED2005 versus placebo in male subjects clinically diagnosed with ED using the EF domain of the IIEF, the Sexual Encounter Profile (SEP) Question 2 and the SEP Question 3. The primary objective will be addressed by estimating the following estimand: difference between treatment policies (each MED2005 dose versus placebo) in all subjects who met the study inclusion/exclusion criteria and who were randomised and attempted intercourse post-randomisation at least once, assessed via the change compared to baseline in EF [IIEF-EF], the ability to achieve vaginal penetration [SEP Question 2] and the ability to have successful intercourse [SEP Question 3] over 12 weeks of treatment

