5. STUDY SYNOPSIS

Protocol Ref: FM57	Study Product: MED2005
Title of the Study: A Phase III, dose-ranging, multi-centre, randomised, double-blind, placebo-controlled, home use, parallel group clinical trial of topically-applied glyceryl trinitrate (GTN) for the treatment of erectile dysfunction (ED) with an open label extension	
Chief Investigator: [name]	
Sites: Approximately 50 investigational sites in countries including Poland, Hungary, Czech Republic, Slovakia, Georgia, Russia, Ukraine, Bulgaria and Latvia.	
Study Period (planned): 2018–2020	Clinical Phase: III
Objectives:	
Primary Objective	

 To demonstrate the efficacy of MED2005 versus placebo in male subjects clinically diagnosed with ED using the erectile function (EF) domain of the International Index for Erectile Function (IIEF), the Sexual Encounter Profile (SEP) Question 2 and the SEP Question 3. The primary objective will be addressed by estimating the following estimand: difference between treatment policies (each MED2005 dose versus placebo) in all subjects who met the study inclusion/exclusion criteria and who were randomised and attempted intercourse post-randomisation at least once, assessed via the change compared to baseline in EF [IIEF-EF], the ability to achieve vaginal penetration [SEP Question 2] and the ability to have successful intercourse [SEP Question 3] over 12 weeks of treatment 	
Secondary Objectives	

 To evaluate the efficacy of MED2005 in male subjects using the Self-Esteem And Relationship (SEAR) questionnaire for men and women, the Global Assessment Questionnaire (GAQ), the additional domains of the IIEF, the Patient Global Impression of Severity (PGI-S), the Patient Global Impression of Change (PGI-C) as well as subjective measures of the time of onset and duration of action (erection) & erection hardness and questions on usage and application of MED2005 To evaluate the long-term (up to 12 months) efficacy of MED2005 To evaluate the safety of MED2005 using adverse events (AEs) and standard physico-chemical assessments 	
Study Design:	
A Phase III, dose-ranging, multi-centre, randomised, double-blind, placebo-controlled, home use, parallel group clinical study to evaluate the efficacy and safety of MED2005, a topically applied GTN gel for the treatment of ED. The study will include a screening period, a double-blind phase and an open-label extension phase.	

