A Bonferroni correction will be used to take into account that there are three active versus placebo comparisons; i.e. all p-values resulting from comparing the three different MED2005 doses (0.6 mg GTN, 1.2 mg GTN, 1.8 mg GTN) versus placebo will be multiplied by three and statistical significance will then be declared if $p < 0.05$. Corresponding Bonferroni corrected 95% confidence intervals will be produced.

Efficacy Analyses:

Double-Blind Phase: Primary and secondary analyses will be performed on the Full Analysis Set (FAS; all randomised subjects who used medication at least once).

The co-primary efficacy endpoints, assessed in the male subjects, are:

- The change from baseline of the average of the Week 4, Week 8 and Week 12 IIEF-EF domain scores
 - The change in percentage of sexual intercourse attempts in which subjects were able to insert their penis into their partner's vagina (SEP Question 2) between baseline and the 12 week treatment period
 - The change in percentage of sexual intercourse attempts in which subjects were able to maintain an erection of sufficient duration to have successful intercourse (SEP Question 3) between baseline and the 12 week treatment period
-

The primary objective will be assessed by testing hypotheses for each MED2005 group (0.6 mg GTN, 1.2 mg GTN or 1.8 mg GTN) separately. The basic statistical model for the primary analysis for all three co-primary endpoints is an analysis of covariance (ANCOVA) including terms for treatment group, site and baseline (as a continuous variable). Baseline ED severity (mild, moderate or severe, based on Visit 2 IIEF-EF) will be included in the analysis of the SEP questions, and will be included in the analysis of IIEF-EF as a sensitivity analysis. The estimated treatment means and differences (MED2005 versus placebo) will be reported as part of this analysis. The objective is for all co-primary endpoints to show superiority of MED2005 to placebo in order to conclude a significant result. No adjustment for multiplicity of the error probability for the individual co-primary endpoints is required. However, the three co-primary endpoints will still be considered in a hierarchy of their importance: IIEF-EF domain, SEP Question 3 and SEP Question 2.

The following secondary efficacy analyses will be performed in a supportive way to describe the effect of treatment:

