14.1 Analysis Sets

The following analysis sets will be used for the statistical analysis of the double-blind phase:

- The **randomised set** will consist of all subjects who were randomised to a treatment
- The **safety set** will consist of all subjects in the randomised set who made use of the medication at least once. In the case of randomisation/treatment errors, subjects will be analysed according to treatment received

- The **full analysis set** (FAS) will consist of all subjects in the randomised set who made use of the medication at least once. In the case of randomisation/treatment errors, subjects will be analysed according to randomised treatment
Primary and secondary analyses will be performed on the FAS.
- The **per protocol set** (PP) will consist of all subjects in the FAS who completed the 12-week treatment period without major protocol violations and who have valid IIEF, SEP Question 2 and SEP Question 3 assessments at Week 12 (Visit 5)

Analysis sets will be identified prior to the unblinding of the study data. The efficacy analysis will be performed as randomised; i.e. a subject will be assigned to the treatment he was initially allocated, irrespective of what treatment was actually applied, and whether or not treatment was discontinued while questionnaire data was collected (see [Section 9.6](#) Withdrawal of Subjects).

In order to assess the consistency of results, sub-group analyses will also be performed according to three subject baseline ED severity groups:

- Mild (IIEF-EF domain score of 17–25)
- Moderate (IIEF-EF domain of 11–16)
- Severe (IIEF-EF domain of ≤ 10)

The following analysis set will be used for the statistical analysis of the open-label extension phase:

- The **open-label analysis set** (OLAS) will consist of all subjects who made use of medication at least once during the open-label extension.

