14.5.2 Handling of Missing Values

Full details on the handling of missing values in analyses of all analysis sets, including rules applied to incomplete questionnaires and planned additional analyses, will be defined in the SAP. Only the main principles are given for the analyses on the FAS here.

Summary statistics will present the number of missing values and then will be based on non-missing values.

Any missing values in efficacy questionnaire data that occur during the treatment period and are then followed by observed data shall be treated as missing at random and imputed using a corresponding multiple imputation approach.

All subjects who are withdrawn from the study will be asked to continue with the IIEF and SEP questionnaires if possible. These data will be used as part of the analysis for estimating the treatment effect over 12 weeks, according to the randomised treatment policy.

There can be remaining missing values for the primary endpoints for subjects who leave the study and provide no further questionnaire data. For these subjects, missing values will be handled using a control-based multiple imputation approach. The imputation model for the missing observations in both the MED2005 and placebo (control) groups will be constructed from the control group only (missing not at random [MNAR]). This assumes that efficacy results post withdrawal, for subjects who withdraw, would have mirrored those seen in the placebo group and thus lose any potential MED2005 treatment benefit.

Additional estimands/tests of treatment effect, beyond the primary treatment policy estimand, may be addressed, including exploring other ways of handling missing values, such as fitting repeated measures mixed models.

Summary statistics will present the number of observed values and will then be based on the non-missing values for the open-label extension phase.

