14.5.3 Primary Analysis

The co-primary efficacy endpoints, assessed in the male subjects, are:

1. The change from baseline of the average of the Week 4, Week 8 and Week 12 IIEF-EF domain scores
2. The change in percentage of sexual intercourse attempts in which subjects were able to insert their penis into their partner's vagina (SEP Question 2) between baseline and the 12 week treatment period
3. The change in percentage of sexual intercourse attempts in which subjects were able to maintain an erection of sufficient duration to have successful intercourse (SEP Question 3) between baseline and the 12 week treatment period

Baseline for the IIEF-EF score is the assessment at Visit 2, baseline for SEP Questions 2 and 3 is the percentage in the screening, treatment free, 4-week period.

The primary objective will be assessed by testing the following hypotheses for each MED2005 dose group (0.6 mg GTN, 1.2 mg GTN or 1.8 mg GTN) and each co-primary endpoint separately, using the FAS:

Null hypothesis (H0): There is no difference in the mean change from baseline in the IIEF-EF domain, SEP Question 2 and SEP Question 3 for the MED2005 treatment group compared with placebo.

$$H0: \mu (\text{MED2005}) = \mu (\text{placebo})$$

Alternative hypothesis (H1): There is a difference in the mean change from baseline in the IIEF-EF domain, SEP Question 2 and SEP Question 3 for the MED2005 treatment group compared with placebo.

$$H1: \mu (\text{active}) \neq \mu (\text{placebo})$$

Each comparison will be carried out at the two-sided 5% level of statistical significance after a Bonferroni correction (p-values multiplied by three). Efficacy will be stated if all null hypotheses for the co-primary endpoints are rejected. However, the three co-primary endpoints will still be considered in a hierarchy of their importance, with the testing order being IIEF-EF domain, SEP Question 3 and SEP Question 2.

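### Does it matter that the primary estimand is defined in eligible men who attempted intercourse, while the primary analysis uses randomised men who used the gel?

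*Protocol*

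**What the plan says.** Section 7.1 sets the primary estimand as a difference between treatment policies, each MED2005 dose against placebo, "in all subjects who met the study inclusion/exclusion criteria and who were randomised and attempted intercourse post-randomisation at least once". The synopsis uses the same population, again requiring that subjects "attempted intercourse post-randomisation at least once, assessed via the change compared to baseline in EF". The target population therefore has three conditions: eligible, randomised, and at least one attempt after randomisation.

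Section 14.1 defines the FAS as "all subjects in the randomised set who made use of the medication at least once", analysed by randomised treatment. It carries no eligibility condition and no attempt condition. Section 14.5.3 tests the hypotheses for each dose "and each co-primary endpoint separately, using the FAS", and the synopsis names the same set for the primary and secondary analyses. Section 14.1 adds that subjects stay in their allocated group "irrespective of what treatment was actually applied, and whether or not treatment was discontinued while questionnaire data was collected".

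Two of the three co-primary endpoints are built on attempts. The one for SEP Question 2 is "The change in percentage of sexual intercourse attempts in which subjects were able to insert their penis" into the partner's vagina, compared between baseline and the 12-week treatment period; SEP Question 3 has the same form. On missing data, 14.5.2 gives main principles only and leaves full details, for all analysis sets, to the SAP.

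**The concern.** An estimand's population and the set used to estimate it should describe the same people, and here they are worded differently. Three groups fall between the two definitions:

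- men randomised in error who used the gel (in the FAS, outside the estimand);
- men who used the gel but never attempted intercourse (in the FAS, outside the estimand);
- eligible men who attempted intercourse but never used the gel (in the estimand, outside the FAS).

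The attempt condition draws most suspicion. An attempt is a post-randomisation event that normally follows application of the gel, so in principle whether it happens could depend on the arm. Conditioning the target population on such an event sits awkwardly beside a treatment-policy comparison. First use of the gel is less exposed: it precedes any drug effect and is made under blinding (10.4.1). At stake would be which population the primary estimate is said to describe and, if the attempt condition were applied in the analysis, some loss of the protection that randomisation gives.

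**Working it through.** **1. Which set is analysed?** The synopsis, 14.1 and 14.5.3 all name the FAS and agree on its definition. No section instructs the analyst to drop FAS men who are ineligible or made no attempt. Anyone following the protocol therefore analyses the same men, whatever 7.1 says.

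**2. How far can the two populations diverge?**

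- *Eligibility.* It is checked before randomisation and dosing (8.1, 9.5, 11.4.2), and the investigator may enrol only eligible men (16.2.2). It is settled before allocation, so it cannot depend on the arm. It describes whom the effect is meant for, and a set that keeps a few men randomised in error can still estimate that effect.
- *Attempt versus gel use.* The gel is applied immediately before intercourse (8.1, 8.2.4), with no more than one tube per intercourse event (10.1). Four attempts are requested in each of three 4-week periods, 3 × 4 = 12 in all. To be in the FAS but outside the estimand on this condition, a man must use the gel and yet make no attempt in 12 weeks. A failed erection does not produce that pattern: SEP Question 1 asks whether any erection was achieved, so the failure is normally recorded as an unsuccessful attempt.
- The protocol gives no rate for any of the three groups, so the discrepancy cannot be turned into a bias on either scale.

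**3. Does the attempt condition do anything useful?** For a man with no treatment-period attempt, the SEP Question 2 and 3 percentages are 0/0. His IIEF-EF score still exists: Questions 3, 4 and 5 score 0, Questions 1 and 2 score 0 to 5 each, and Question 15 scores 1 to 5, giving 1 to 15. The attempt condition thus keeps two of the three co-primary variables defined throughout the target population. Removing it would create a case that then needs its own rule.

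**4. Would rewording change the design figures?** Inputs from 14.7: n = 250 per group; differences 3.2, 11.5 and 12; SDs 5.6, 33 and 33; correlations 0.5, 0.5 and 0.6; two-sided alpha 0.05/3 = 0.01667, critical value 2.394.

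For each endpoint, power = Φ(δ / (SD·√(2/n)) − 2.394), with √(2/250) = 0.0894:

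| Endpoint | δ / (SD·√(2/n)) | Power |
|---|---|---|
| IIEF-EF | 3.2 / 0.501 = 6.39 | >99.9% |
| SEP Question 2 | 11.5 / 2.952 = 3.90 | 93.35% |
| SEP Question 3 | 12 / 2.952 = 4.07 | 95.27% |

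The trivariate normal probability that all three statistics exceed 2.394 is 90.4%, and the smallest n giving 90% is 248 per group. The stated 90% at 250 is reproduced. None of these inputs depends on the wording of 7.1.

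**5. Is there an obviously better alignment?** Deleting both conditions from 7.1 leaves all randomised subjects, which is the randomised set of 14.1 and still not the FAS. To match on that wording, the primary analysis would have to move to the randomised set. As an illustration, assume a proportion of each arm never uses the gel:

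| Assumed never using gel | Joint power, FAS (non-users dropped) | Joint power, all randomised (zero effect in non-users) |
|---|---|---|
| 0% | 90.4% | 90.4% |
| 2% | 89.7% | 88.9% |
| 5% | 88.5% | 86.3% |
| 10% | 86.2% | 81.2% |

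The proportions are assumptions; the protocol gives none. The table shows only that the choice of set involves a trade-off. Writing the FAS definition into 7.1 would also align the two, but it changes no analysis.

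**The case for a change.** The strongest case for a change is that this is a contradiction and not an omission. The protocol fixes both populations itself, in different words, and what it defers to the SAP is analysis detail and missing-data handling, not the target population. Headache and hypotension are known effects of GTN (6.4.2), so an arm-dependent route to making no attempt can be imagined. Replacing the attempt condition with gel use in two places costs almost nothing. There is also a gap behind it: 14.5.2 covers missing values followed by observed data, and it says "There can be remaining missing values for the primary endpoints for subjects who leave the study and provide no further questionnaire data", but a man who stays in the study and never attempts is neither.

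Much of this stands as description. The wording does conflict, and using one phrase throughout would be tidier. It does not establish a defect in the analysis. The arm-dependent route matters only if attempters are selected for analysis, and the plan does not select them. A treatment-policy strategy does not by itself forbid restricting the population, and the FAS has its own post-randomisation condition in gel use. The rule for men who stay without attempting is missing-data detail that 14.5.2 expressly leaves to the SAP, which is not at hand, so its absence from the protocol cannot be counted as an error.

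**Conclusion.** The mismatch is genuine but is one of wording, and no change to the plan follows. Followed as written, the protocol leads every analyst to the same set (the FAS), the same comparison by randomised arm, the same sample size and the same joint power of about 90%. Aligning the objective with the FAS would alter no result. How best to align them (FAS, all randomised, or attempters) is open to reasonable debate, and each option has a cost.

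The size of the remaining difference cannot be computed from the document. The judgement that it is small rests on the close link between applying the gel and attempting intercourse, on the eligibility checks before randomisation, and on failed erections being recorded as attempts. It would need revisiting if the blinded data review showed more than a handful of men who used the gel and recorded no attempt. How those men, and any men randomised in error, enter the analysis is a detail that the SAP can reasonably supply before unblinding.
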